2.3. Benefit-Risk Assessment

2.3.1. Risks for Study Participation

Cardiac Arrhythmias

Atrial fibrillation, atrial flutter, and cases of ventricular tachyarrhythmia including some fatal events, have been reported in participants treated with ibrutinib, particularly in participants with

cardiac risk factors, hypertension, acute infections, and a previous history of cardiac arrhythmia. Participants will be periodically monitored for cardiac arrhythmia. Participants who develop arrhythmic symptoms (eg, palpitations, lightheadedness, syncope, chest discomfort, or new onset dyspnea) should be evaluated clinically, and if indicated, have an ECG performed. For cardiac arrhythmias which persist, consider the risks and benefits of ibrutinib treatment, and follow the dose modification guidelines.

Bleeding-related Events

There have been reports of bleeding events in participants treated with ibrutinib, both with and without thrombocytopenia. These include minor bleeding events such as contusion, epistaxis, and petechiae; and major bleeding events, some fatal, including gastrointestinal (GI) bleeding, intracranial hemorrhage, and hematuria. In an in vitro platelet function study, inhibitory effects of ibrutinib on collagen induced platelet aggregation were observed.

Use of either anticoagulants or antiplatelet agents concomitantly with ibrutinib increases the risk of major bleeding. A higher risk for major bleeding was observed with anticoagulant than with antiplatelet agents. The risks and benefits of anticoagulant or antiplatelet therapy should be considered when coadministered with ibrutinib. Signs or symptoms of bleeding should be monitored. Supplements such as fish oil and vitamin E preparations should be avoided. Ibrutinib should be held at least 3 to 7 days pre- and postsurgery depending upon the type of surgery and the risk of bleeding. Participants with congenital bleeding diathesis have not been studied.

Cytopenias

Treatment-emergent Grade 3 or 4 cytopenias (neutropenia, thrombocytopenia, and anemia) were reported in participants treated with ibrutinib. Complete blood counts should be monitored carefully.

Diarrhea

Diarrhea is the most frequently reported nonhematologic AE with ibrutinib monotherapy and combination therapy. Participants should be monitored carefully for gastrointestinal AEs and cautioned to maintain fluid intake to avoid dehydration. Medical evaluation should be made to rule out other etiologies such as *Clostridium difficile* or other infectious agents. For participants with severe and prolonged symptoms, ibrutinib should be considered to follow dose modification guidelines (see Section 6.1.1).

Infections

Infections (including sepsis, bacterial, viral, or fungal infections) were observed in participants treated with ibrutinib therapy. Some of these infections have been associated with hospitalization and death. For participants who are at increased risk for opportunistic infections prophylaxis should be considered according to the standard of care. Although causality has not been established, cases of progressive multifocal leukoencephalopathy and hepatitis B reactivation have occurred in participants treated with ibrutinib. Participants should be monitored for signs and symptoms (fever, chills, weakness, confusion, vomiting, and jaundice) and appropriate therapy should be instituted as indicated.

Interstitial Lung Disease

Cases of interstitial lung disease (ILD) have been reported in participants treated with ibrutinib. Participants will be monitored for pulmonary symptoms indicative of ILD. In case of onset of symptoms, ibrutinib will be interrupted and ILD will be managed appropriately. If symptoms persist, the risks and benefits of ibrutinib treatment should be considered and the dose modification guidelines should be followed.

Nonmelanoma Skin Cancer

Nonmelanoma skin cancers have occurred in participants treated with ibrutinib. Participants will be monitored for the appearance of nonmelanoma skin cancer.

Rash

Rash has been commonly reported in participants treated with either single agent ibrutinib or in combination with chemotherapy. Rash occurred at a higher rate in the ibrutinib arm than in the ofatumumab arm in study PCYC-1112-CA. Most rashes were mild to moderate in severity. Isolated cases of severe cutaneous adverse reactions (SCARs) including Stevens-Johnson syndrome (SJS) have been reported in participants treated with ibrutinib. Participants should be closely monitored for signs and symptoms suggestive of SCAR including SJS. Participants receiving ibrutinib should be observed closely for rashes and treated symptomatically, including interruption of the suspected agent as appropriate. In addition, hypersensitivity-related events including erythema, urticaria, and angioedema have been reported.

Hypertension

Hypertension has been commonly reported in participants treated with ibrutinib. Participants will be monitored for any new onset of hypertension or hypertension that is not adequately controlled after starting ibrutinib. Adjust existing antihypertensive medications and/or initiate antihypertensive treatment as appropriate.

Tumor Lysis Syndrome

Tumor lysis syndrome has been reported with ibrutinib therapy. Patients at risk of tumor lysis syndrome are those with high tumor burden prior to treatment. Participants will be closely monitored and appropriate precautions will be taken.

Risks Relevant With Rituximab

Tumor flare (IgM flare) has been reported after initiation of rituximab therapy for the patients with WM (see Section 5.3 and Section 6.1.2.5). Refer to the current rituximab label for detailed information on risks of rituximab.²⁹

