6.1.1.2. Dose Hold, Reduction or Discontinuation of Ibrutinib

Treatment with ibrutinib should be withheld for any unmanageable, potentially ibrutinib-related nonhematological toxicity that is ≥Grade 3 in severity and any hematologic toxicity meeting the criteria in Section 6.1.1.3. Ibrutinib may be withheld for a maximum of 28 consecutive days for toxicity. Ibrutinib should be discontinued in the event of a toxicity lasting >28 days, unless reviewed and approved by the Medical Monitor.

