6.1.1.3. Dose Modification for Adverse Reactions

The dose of ibrutinib should be modified according to the dose modification guidance in [Table 2](#) or [Table 3](#) if any of the following drug-related toxicities occur:

Refer to [Table 2](#)

- Grade 3 or greater neutropenia with infection or fever

- Grade 4 ANC (<500/ μ L) for >7 days
- Grade 3 thrombocytopenia (platelets <50,000/ μ L) in the presence of \geq Grade 2 bleeding events
- Grade 4 thrombocytopenia (platelets <25,000/ μ L)
- Grade 3 or 4 nausea, vomiting, or diarrhea if persistent, despite optimal antiemetic and/or antidiarrheal therapy
- Any other Grade 4 or unmanageable Grade 3 toxicity attributed to ibrutinib (except events specified in [Table 3](#))

Refer to [Table 3](#)

- Grade 2 or higher cardiac failure and Grade 3 or higher cardiac arrhythmias

For Grade 3 or 4 atrial fibrillation or persistent atrial fibrillation of any grade, consider the risks and benefits of ibrutinib treatment. If clinically indicated, the use of anticoagulants or antiplatelet agents may be considered for the thromboprophylaxis of atrial fibrillation (Section [6.5.2.3](#)).

Table 2: Ibrutinib Dose Modifications for Events not Specified in [Table 3](#)

Occurrence	Action to be Taken
First	Withhold ibrutinib until recovery to Grade \leq 1 or baseline; may restart at original dose level ^a
Second	Withhold ibrutinib until recovery to Grade \leq 1 or baseline; may restart at 1 dose level lower (ie, 280 mg/day / 2 capsules)
Third	Withhold ibrutinib until recovery to Grade \leq 1 or baseline; may restart at 1 dose level lower (ie, 140 mg/day / 1 capsule)
Fourth	Discontinue ibrutinib ^b

^a When resuming treatment, restart at the same or lower dose based on benefit risk evaluation. If the toxicity reoccurs, reduce daily dose by 140 mg.

^b If the oral ibrutinib is discontinued for toxicity, participant will end the treatment phase of the study.

Table 3: Ibrutinib Dose Modifications for Cardiac Failure or Cardiac Arrhythmias

Events	Occurrence	Action to be Taken
Grade 2 cardiac failure	First	Withhold ibrutinib until recovery to Grade \leq 1 or baseline; restart at 1 dose level lower (ie, 280 mg/day / 2 capsules)
	Second	Withhold ibrutinib until recovery to Grade \leq 1 or baseline; restart at 1 dose level lower (ie, 140 mg/day / 1 capsule)
	Third	Discontinue ibrutinib ^b

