- The investigator should consider the risk/benefit of continuing ibrutinib based on the nature and status of the participant's underlying condition and the potential risks associated with COVID-19.
- As with all infections, the investigator should follow the protocol guidance which is to interrupt therapy for Grade 4 or unmanageable Grade 3 toxicity (see Section 6.1.1.3), and resume once infection has resolved to Grade 1 or baseline (recovery). Given that severe acute respiratory syndrome coronavirus 2 (SARS-CoV-2) is a new pathogen, a more cautious approach would be appropriate, with interruption for confirmed cases of SARS-CoV-2 infection of any grade.

On-site Monitoring Visits

In case on-site monitoring visits are not possible, as per institution policies, the sponsor's site managers may contact the investigator to arrange remote monitoring visits. Additional on-site monitoring visits may be needed in the future to catch up on source data verification.

All of the above measures are recommended for consideration on a temporary basis during the COVID-19 pandemic to enable continuity of treatment and to ensure that participant assessments, particularly those assessing relapse and safety, continue as outlined in the protocol without imposing health risk to participants, their families, and site staff. Every effort should be made to complete all protocol-required assessments. Investigators should use their clinical judgment and risk/benefit assessment in determining if a participant can continue study intervention in the absence of on-site clinic visits. If remote visits are not possible, or if in the investigator's judgment, appropriate safety monitoring is not feasible in a remote setting, the investigator should consider temporarily interrupting study intervention (for a maximum of 28 consecutive days, unless reviewed and approved by the sponsor) or discontinuing study intervention.

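### The ILD interruption stated in Section 2.3.1 is not carried into the ibrutinib hold rules of Section 6, and 6.1.1.2 gives a narrower hold trigger than 6.1.1.3 and Table 3

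*Protocol*

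**What the plan says.** Three places in the protocol bear on when ibrutinib is interrupted for toxicity.

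- **Section 2.3.1, Interstitial Lung Disease.** The instruction is firm: "In case of onset of symptoms, ibrutinib will be interrupted and ILD will be managed appropriately". The next sentence deals with what follows: "If symptoms persist, the risks and benefits of ibrutinib treatment should be considered and the dose modification guidelines should be followed".
- **Section 6.1.1.2.** The general hold rule is: "Treatment with ibrutinib should be withheld for any unmanageable, potentially ibrutinib-related nonhematological toxicity that is ≥Grade 3 in severity". The same sentence sends the reader to 6.1.1.3 for hematologic toxicity, and for nothing else.
- **Section 6.1.1.3 with Tables 2 and 3.** Doses are modified "if any of the following drug-related toxicities occur". After the hematologic and gastrointestinal entries, the list closes with a catch-all, "Any other Grade 4 or unmanageable Grade 3 toxicity attributed to ibrutinib", which excepts the Table 3 events. The entry for Table 3 is "Grade 2 or higher cardiac failure and Grade 3 or higher cardiac arrhythmias".

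Section 6.1 tells sites to follow the dosing and toxicity guideline set out in that section. Section 6.6 places the ibrutinib dose-modification details in 6.1.1.3 and 6.1.1.4. Appendix 10 restates the general rule as "interrupt therapy for Grade 4 or unmanageable Grade 3 toxicity (see Section 6.1.1.3". None of these refers back to 2.3.1.

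**The concern.** Section 2.3.1 presents the ILD interruption as something that will happen, and Section 2.3.3 rests the benefit-risk conclusion partly on the measures taken to limit risk. A site using the dosing section as directed would not come across this measure, because Section 6 does not mention ILD.

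Section 6 itself describes the nonhematological hold in two ways. A reader of 6.1.1.2 alone gets a narrower trigger than a reader of 6.1.1.3 and Table 3.

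What is at stake is consistent handling of safety events across sites. Safety is a secondary objective, and Section 9.4.4 tabulates ibrutinib exposure and reasons for discontinuation. With a target of 14 participants, one participant is 1/14 = 7.1% of the denominator, so a single event handled differently would be visible in those tables.

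**Working it through.** No arithmetic bears on the finding; the check is a comparison of text.

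**1. Is ILD named in the operative section?** No. It is absent from 6.1.1.2, 6.1.1.3, Table 2 and Table 3. It can reach a hold only through the general rule in 6.1.1.2 or the catch-all in 6.1.1.3.

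**2. Triggers side by side, for symptomatic ILD attributed to ibrutinib.**

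| ILD event | 2.3.1 | 6.1.1.2 | 6.1.1.3 |
|---|---|---|---|
| Below Grade 3 | interrupt | no trigger | no trigger |
| Grade 3, manageable | interrupt | no trigger | no trigger |
| Grade 3, unmanageable | interrupt | hold | hold |
| Grade 4, manageable | interrupt | no trigger | hold |
| Grade 4, unmanageable | interrupt | hold | hold |

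Section 2.3.1 goes further than both operative rules in the first two rows. The two operative rules differ from each other in the fourth.

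**3. What happens after the interruption?** Section 2.3.1 sends persistent symptoms to the dose modification guidelines. Table 2, which gives the recovery grade and restart level, is reached through the 6.1.1.3 triggers. An ILD interruption in the first two rows meets none of them, so no restart step is assigned. The 28-day ceiling on holds in 6.1.1.2 is worded for toxicity in general and would still apply.

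**4. Is 2.3.1 only background?** Other measures named there do reappear in operative text. Diarrhea has an entry in 6.1.1.3, arrhythmia has Table 3, and perioperative holds are in 5.3. ILD is the one toxicity for which 2.3.1 says that ibrutinib will be interrupted, and it has no counterpart in Section 6.

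**5. 6.1.1.2 against 6.1.1.3 and Table 3.** The first requires both unmanageability and Grade 3 or higher. Three classes lie outside that and are acted on by the second:

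- manageable Grade 4 nonhematological toxicity, through the catch-all;
- Grade 2 cardiac failure, through Table 3, below the Grade 3 floor of 6.1.1.2;
- Grade 3 arrhythmia that is manageable, since Table 3 sets no manageability condition.

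**6. Causality wording.** Section 2.3.1 sets no condition. Section 6.1.1.2 requires a potential relation to ibrutinib. Section 6.1.1.3 requires that the toxicity be drug-related and, in its catch-all, attributed to ibrutinib.

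**The case against.** The strongest reply is that nothing here is a contradiction in the strict sense. Neither 6.1.1.2 nor 6.1.1.3 says that its conditions are the only ones, and neither tells a site to continue below its threshold. A site that applied the broadest trigger would satisfy every passage. This stands. A reader might infer that Section 6 orders continuation through early ILD; it does not, because silence is not an instruction to continue.

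The general rules are also plainly not exhaustive. Event-specific holds appear in 5.3 (surgery), 6.1.1.4 (hepatic impairment), 6.5.2.1 (strong CYP3A inhibitors), 6.5.2.3 (therapeutic anticoagulation) and Appendix 10 (confirmed SARS-CoV-2 infection). An ILD instruction in 2.3.1 could be read in the same way, and investigators must follow the whole protocol. That is fair, but those holds all stand in sections that govern conduct. The ILD instruction stands in the introduction, and nothing in Section 6 points to it.

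Section 2.3.1 can also be read as a sequence, with interruption first and the general guidelines afterwards. This explains the order of the steps but does not supply the missing restart step. Section 7.1 provides for stopping study intervention when the investigator judges that safety requires it, but that is a judgement about discontinuation and does not do the work of a stated interruption.

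On the second part, Table 3 expressly governs the cardiac events, and the catch-all excepts them. A reader might infer that 6.1.1.2 permits continuation through Grade 2 cardiac failure. That would mean ignoring the table written for that event. For Grade 4 toxicity, Appendix 10 confirms the 6.1.1.3 wording. What remains is that 6.1.1.2 summarises the rule too narrowly and limits its cross-reference to hematologic toxicity.

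**Conclusion.** The point holds as a mismatch of safety triggers. For symptomatic ILD short of Grade 4 or unmanageable Grade 3, Section 2.3.1 calls for interruption, while Section 6 contains neither a trigger nor a restart step. Independently, 6.1.1.2 is narrower than 6.1.1.3 and Table 3 in three event classes.

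The conclusion assumes that sites work from Section 6, as Sections 6.1 and 6.6 direct. Its practical size cannot be given, because the protocol states neither ILD incidence nor ILD-specific grade definitions. In particular, it does not establish at which grades ILD counts as symptomatic. The sample size, the power and the overall response rate analysis do not depend on any of this. It should be corrected because it concerns a stated safety measure and is cheap to correct. No view is taken on which threshold is clinically right.

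**What to change.** Reconcile Sections 2.3.1, 6.1.1.2 and 6.1.1.3 with Tables 2 and 3 so that:

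- the ILD instruction, including what follows an interruption, reads the same wherever it appears;
- the hold triggers and their causality wording agree;
- 6.1.1.2 refers to 6.1.1.3 and Tables 2 and 3 for all toxicities, hematologic or not.

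Whether the introduction or the dosing section changes is for the sponsor's clinical team to decide. The restatement in Appendix 10 should be checked against the result. The cost is a short wording amendment, with no change to the sample size or the planned analyses.

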2.3.2. Benefits for Study Participation

In study PCYC-1118E, ibrutinib monotherapy resulted in high rates of response (\geq PR); the responses were rapid and durable and improved over time. Most subjects were progression-free and alive at 18 months. In study PCYC-1127-CA, treatment with ibrutinib in combination with rituximab had high overall response and improvement of PFS in participants with treatment naïve

and previously treated WM. Considering the results of studies PCYC-1118E and PCYC-1127-CA, the participants may benefit from treatment outcome observed in this study.

2.3.3. Benefit-Risk Assessment for Study Participation

Taking into account the measures taken to minimize risk to participants participating in this study, the potential risks identified in association with ibrutinib are justified by the anticipated benefits that may be gained in participants with treatment naïve or relapsed/refractory WM.

3. OBJECTIVES AND ENDPOINTS

Objectives	Endpoints
Primary	
 To evaluate ORR by IRC assessment, when combined with rituximab in Japanese participants with treatment naïve or relapsed/refractory WM. The ORR is defined as the proportion of participants with CR, VGPR, or PR (ie, \geqPR) by IRC assessment. Response will be defined by the modified sixth IWWM (NCCN version 2, 2019).²⁷
Secondary	
 To assess PFS by IRC assessment. PFS is defined as duration from the date of initial dose of ibrutinib to the date of disease progression or death, whichever occurs first. To determine the PK of ibrutinib in combination with rituximab in Japanese participants with treatment naïve or relapsed/refractory WM. PK parameters of ibrutinib and metabolite PCI-45227 (if possible and judged relevant). To explore biomarkers identified from other studies of ibrutinib in samples collected for MYD88 and CXCR-4 assessments. Prognostic biomarkers relative to disease and/or treatment outcomes including MYD88 and CXCR-4. To evaluate safety of ibrutinib, when combined with rituximab in Japanese participants with treatment naïve or relapsed/refractory WM. Safety parameters of ibrutinib, including AEs and clinical laboratory assessments.

Keys: AE adverse event; CR complete response; CXCR 4 C X C chemokine receptor type 4; IRC independent review committee; IWWM International Workshop on Waldenstrom's Macroglobulinemia; MYD88 myeloid differentiation primary response gene 88; NCCN National Comprehensive Cancer Network; ORR overall response rate; PFS progression free survival; PK pharmacokinetics; PR partial response; VGPR very good partial response; WM Waldenstrom's Macroglobulinemia.

Refer to Section 8, Study Assessments and Procedures for evaluations related to endpoints.

HYPOTHESIS

The primary hypothesis of this study is that ibrutinib in combination with rituximab is an effective agent in Japanese participants with treatment naïve or relapsed/refractory WM as measured by an ORR (the lower bound of exact 95% CI based on binomial distribution $>32\%$).

4. STUDY DESIGN

4.1. Overall Design

This is an open-label, single arm, multicenter Phase 2 study to evaluate the efficacy and safety of ibrutinib 420 mg in combination with rituximab in Japanese participants (≥ 20 years of age) with treatment naïve or relapsed/refractory WM.

The participation period will consist of a screening phase, a treatment phase, and a follow-up phase. The screening phase assessments will be performed ≤ 30 days prior to study intervention initiation. In this study, eligible participants will have clinicopathological diagnoses of WM in accordance with the consensus panel of the second IWWM. Pathologic diagnosis will also be reviewed by a central pathologist (see Section 8.4.7).²⁸

The treatment phase will extend from first dose of ibrutinib until the EOT visit (which should occur after 30 days of last dose of ibrutinib or prior to the start of a new anticancer treatment). All participants will receive IV administration of rituximab weekly for 4 consecutive weeks, followed by a second course of IV rituximab administered weekly for 4 consecutive weeks after a 12-week interval. All participants will receive oral ibrutinib daily and continuously until criteria for permanent discontinuation of ibrutinib are met (see Section 7.1, Discontinuation of Study Intervention). Response assessments will be performed using the modified consensus criteria adapted from the sixth IWWM (NCCN version 2, 2019).²⁷ Participants with confirmed PD must discontinue the study intervention.

The primary efficacy endpoint is ORR by IRC assessment in Japanese participants with treatment naïve or relapsed/refractory WM when ibrutinib is combined with rituximab. Overall response rate is defined as the proportion of participants who achieve CR, VGPR, or PR according to modified sixth IWWM (NCCN version 2, 2019).²⁷

A clinical cutoff of the primary endpoint, ORR ($\geq PR$), will be conducted at the time when all the participants complete assessment of Week 57 or EOT visit. The response evaluable population is defined as all enrolled participants who have measurable disease at baseline, received at least 1 dose of ibrutinib, and have at least 1 adequate postbaseline disease assessment for responses (consecutive assessments are required for the CR, VGPR, PR, and MR except radiology assessment and bone marrow). Adequate disease assessment is defined as having sufficient evidence to correctly indicate that progression has or has not occurred. Participants who died due to progression are also considered to have had adequate assessment. At the same time, secondary endpoints will be evaluated.

The ORR in patients in the ibrutinib plus rituximab arm and in the placebo plus rituximab arm from the PCYC-1127-CA study were 72% and 32%, respectively. Assuming an expected ORR of 72% for the current study, 14 participants are needed to demonstrate that the lower limit of exact 2-sided 95% CI of estimated ORR exceeds 32% with 80% power.

In order to maintain the study population as similar as possible to study PCYC-1127-CA, the number of both treatment naïve WM patients and relapsed/refractory WM patients in this study should be at least 6 participants for each subpopulation.

An IRC and an external safety monitoring committee will be commissioned for this study. Refer to Committees Structure in Section 10.3, Appendix 3, Regulatory, Ethical, and Study Oversight Considerations for details.

Blood samples will be collected to assess the PK and biomarkers as described in Sections 8.8 and 8.10, respectively.

A diagram of the study design is provided in Section 1.2, Schema.

